8.1 Risks and Benefits	16
8.1.1 Potential benefits	16
8.1.2 Potential harms	16
9. MONITORING.....	17
9.1 Institutional Review Board (IRB).....	17
9.2 Data Safety and Monitoring Board (DSMB).....	17
10 CLINICAL MONITORING PLAN	17
11. FUNDING	17
12. DATA SHARING	18
References	19

SYNOPSIS

The “The “Thiamine for Renal Protection in Septic Shock (TRPSS)” study is a randomized, clinical trial that aims to determine the impact of Thiamine vs. Placebo on kidney injury in patients with septic shock. The trial will be conducted in accordance with all applicable national and international laws, regulations, and guidelines. The trial and this protocol is developed in accordance with the International Conference on Harmonization (ICH) guidelines¹⁻³ and the Standard Protocol Items: Recommendations for Interventional Trials (SPIRIT) statement^{4,5}. The principal investigator wrote the protocol with input from the steering committee. Any substantial changes or amendments to the protocol will be clearly documented and communicated to all relevant parties.

TRIAL OVERVIEW

Title Thiamine for Renal Protection in Septic Shock (TRPSS)

Clinical Trials Number	NCT03550794
Sources of monetary or material support	National Institute of General Medical Sciences
Study Sites	Beth Israel Deaconess Medical Center, Long Island Jewish Medical Center, North Shore Medical Center
Condition studied	Septic Shock
Interventions	Thiamine 200mg IV twice daily for 3 days
Comparator	Placebo
Inclusion criteria	
1) Adult \geq18 years of age2) Suspected or Confirmed Infection (defined as collection of a blood/fluid culture and provision of an antimicrobial)3) Receipt of a vasopressor agent (e.g. norepinephrine, phenylephrine, vasopressin)4) Serum lactate \geq2mmol/L5) Creatinine $>$1.0mg/dL
Exclusion criteria	
1) Clinical indication for thiamine administration (alcoholism, known or highly suspected deficiency) or treatment with thiamine beyond the amount found in a standard multivitamin within the last 10 days2) Renal replacement therapy within the past 30 days3) Comfort measures only or anticipated withdrawal of support within 24 hours4) Protected populations (pregnant women, prisoners)5) Known thiamine allergy
Study type	Interventional Allocation: Randomized (1:1) Intervention model: Parallel group Masking: Double-blind
Target sample size	88 Participants (44/arm)
Primary outcome	Change in creatinine over the first 72-hours after enrollment
Key secondary outcomes	
• Incidence of renal failure requiring renal replacement during index ICU stay• Length of ICU stay• Hospital mortality

STEERING COMMITTEE

[name].

Attending, Pulmonary and Critical Care Medicine
Beth Israel Deaconess Medical Center
Harvard Medical School

[name].

Associate Professor of Medicine
Director, Center for Resuscitation Science
Beth Israel Deaconess Medical Center
Harvard Medical School

[name]

Assistant Professor of Emergency Medicine
Beth Israel Deaconess Medical Center
Harvard Medical School

[name].

Assistant Professor of Medicine
Beth Israel Deaconess Medical Center
Harvard Medical School

[name].

Instructor in Emergency Medicine
Beth Israel Deaconess Medical Center
Harvard Medical School

[name]

Associate Professor of Medicine
Beth Israel Deaconess Medical Center
Harvard Medical School

Conflicts of interest

The members of the steering committee have no financial conflicts of interest related to the current trial.

1. BACKGROUND AND SIGNIFICANCE

1.1 Scope of the Problem

The worldwide incidence of sepsis has been estimated at more than 23 million cases⁶ and sepsis contributes to more than a third of all hospital deaths in the United States.^{7,8} Mortality for those in septic shock with elevated lactate is more than 40%.⁹ In addition to high short-term mortality, sepsis is associated with significant post-discharge morbidity and mortality.¹⁰⁻¹⁵ The economic burden for participants suffering from sepsis is staggering with an estimated yearly financial burden of \$17 billion.¹⁶ Treatments are generally limited to antibiotics and intravenous fluids while providing support to maintain organ function.^{17,18}

1.2 Existing Interventions

To date, numerous interventions have been tested for participants with sepsis and septic shock with limited, if any, success.¹⁹⁻²² Recently, three large studies found no benefit from early goal directed therapy over usual care in emergency department participants with sepsis.²³⁻²⁵ Other recent studies focusing on hemodynamics, fluid therapy, and transfusions have also failed to show a significant benefit in this participant population.²⁶⁻²⁸ Previous studies focusing on immunomodulatory therapies or drotrecogin alfa have likewise shown disappointing results.²⁹⁻³⁵

1.3 Renal failure is a common sequela of septic shock and is associated with poor outcomes. Renal failure has been estimated to occur in 23% of patients with severe sepsis and 51% of patients with septic shock.³⁶ Further, the development of renal failure during sepsis or septic shock portends a significantly worse outcome.³⁶ In one study of patients with septic shock, there was a step-wise increase in mortality with worsening AKI.³⁷ These data suggest that attenuating kidney injury in sepsis will improve outcomes.

1.4 Thiamine (vitamin B1) is an essential component of mitochondrial energy production and may reduce oxidative stress. Thiamine is a key component in aerobic metabolism, working as a cofactor for pyruvate dehydrogenase. When thiamine levels are insufficient, pyruvate is unable to enter the Krebs Cycle, and pyruvate is converted to lactate, rather than acetyl-coenzyme A.^{24,25} Relative thiamine deficiency, therefore, causes a shift in metabolism to the anaerobic pathway, resulting in elevated serum lactate levels. Thiamine is also a critical component of the pentose phosphate pathway, which may reduce oxidative stress.^{9,10} As the kidney maintains a high mitochondrial abundance relative to other organs,⁸ it may be especially susceptible to perturbations in mitochondrial function.

1.5 Thiamine may attenuate renal injury in patients with septic shock. In a *post-hoc* analysis of data collected during a randomized trial of thiamine vs. placebo,³ patients who received thiamine were less likely to require renal replacement therapy (RRT) and had lower creatinine levels over time as compared to patients who received placebo.⁴ That study, however, was limited by its *post-hoc* design, an imbalance in premorbid renal function between groups, and inconsistency with regards to the timing of biomarker measurement. In a non-randomized observation study of patients with severe sepsis or septic shock at a single center, those who received the combination of thiamine, vitamin C, and hydrocortisone were less likely to require RRT as compared to historical controls at the same site (3/31 [10%] vs. 11/30 [33%], $p=0.02$).²⁶ This study likewise provides some support for thiamine as a renal protective agent in sepsis, but is limited by its quasi-experimental design and the associated potential for bias.

2. TRIAL DESIGN

2.1 Overview

This will be an investigator-initiated, randomized, placebo-controlled, parallel group, double-blind, superiority trial of thiamine vs. placebo in participants with septic shock. A total of 88 adult participants will be enrolled. The primary outcome will be the change serum creatinine between enrollment and 72-hours. Key secondary outcomes include the incidence of renal failure during the index ICU stay and survival at 30 days.

2.2 Allocation

Participants will be randomized in a 1:1 ratio to either thiamine or placebo in blocks with random sizes of 2 or 4. The randomization will be stratified according to site.³⁸ An independent statistician will create the randomization list using a random number generator. The complete list will only be shared with an independent pharmacy consultant, who will not be involved in clinical care. The pharmacy consultant and the independent statistician will both store the randomization list.

2.3 Intervention

2.3.1 Thiamine

The study drug will consist of thiamine 200mg in 50ml of 0.9%NACL saline solution given parenterally every 12 hours for 3 days.

2.3.2 Placebo

The placebo will consist of matching volumes of normal saline (0.9% NaCl).

2.4 Blinding

The trial will be double-blind; participants, investigators, and the clinical team will be blinded to the allocation. Only the pharmacy providing the study drug will be aware of the allocation. The pharmacy will not be involved with clinical care or outcome evaluation.

Vitamin B1 is not known to have distinctive rapid effects or other characteristics which could lead to unblinding.

The decision to unblind will be at the complete discretion of the treating physician and clinical team. If a clinical team wishes to unblind a participant (e.g. if anaphylaxis occurs), they will contact the research pharmacy who will reveal the study group to the clinical team (but the research team will remain blinded). However, we do not expect many scenarios where emergency unblinding will be necessary. In case unblinding occurs, the reason(s) will be clearly documented in the case report form. The patient will no longer receive study medications, but will be followed for outcomes.

2.5 Regulatory Issues

An Investigational New Drug (IND) application was submitted to and approved by the Food and Drug Administration (FDA) for this study (IND # 107, 135).

The trial has been registered on ClinicalTrials.gov: NCT03550794

3.2 Inclusion criteria

Inclusion criteria:

- 1) Adult ≥ 18 years of age
- 2) Suspected or Confirmed Infection (defined as collection of a blood/fluid culture and provision of an antimicrobial)
- 3) Receipt of a vasopressor agent (e.g. norepinephrine, phenylephrine, vasopressin)
- 4) Serum lactate ≥ 2 mmol/L
- 5) Creatinine >1.0 mg/dL

3.3 Exclusion criteria

Exclusion criteria:

- 1) Clinical indication for thiamine administration (alcoholism, known or highly suspected deficiency) or treatment with thiamine beyond the amount found in a standard multivitamin within the last 10 days
- 2) Renal replacement therapy within the past 30 days
- 3) Comfort measures only or anticipated withdrawal of support within 24 hours
- 4) Protected populations (pregnant women, prisoners)
- 5) Known thiamine allergy

Justification of Inclusion and Exclusion Criteria: The inclusion criteria reflect the definition of septic shock put forth by the Society of Critical Care Medicine and European Society of Intensive Care Medicine Task Force.¹⁶ We will include only patients with a creatinine of >1.0 mg/dL to ensure we are evaluating a true 'at-risk' population for kidney injury. The trial end-points cannot be assessed in patients already receiving renal replacement therapy, and this population will therefore be excluded. We have chosen to include adult patients only due to differences in etiology and treatment of septic shock in children. Also, BIDMC does not have a pediatric unit. We will exclude patients who are presently receiving or who will likely receive supplemental thiamine for clinical purposes as we feel it would be unethical to randomize these patients to the placebo arm. We will also exclude patients with a known thiamine allergy.

4. TRIAL PROCEDURES

4.1 Participant Identification

Screening will be performed in the emergency department and intensive care units (ICUs) with the assistance of electronic screening mechanisms. Detailed screening logs, with reason(s) for exclusion will be kept at each site and reported in the final publication.

4.2 Consent procedures

Informed, written consent will be obtained for all participants prior to enrollment.

After it is determined that they meet all inclusion criteria and no exclusion criteria, the participant (or legally authorized representative [LAR] if the participant is not able to provide consent) will be approached for written informed consent by a physician co-investigator from the team. The

investigator will provide the participant/representative information regarding the background and significance of the study, eligibility criteria, and a description of the protocol. To ensure we are correctly identifying the potential participant's LAR, we communicate with members of the clinical team. The consent process may need to be modified based on site-specific IRB recommendations.

The name of the study investigator obtaining consent will be clearly documented, and this person will sign the informed consent document and provide the date and time of their signature. If a physician is performing remote consent, then a copy of the consent form will be signed as soon as he/she is physically present. Signed copies of the consent form will be given to the participant/surrogate, and the original consent document will be stored in the secure study file. In obtaining and documenting informed consent, each investigator will comply with the applicable regulatory requirements and adhere to the ethical and Good Clinical Practice principles that have their origin in the Declaration of Helsinki.

4.3 Randomization

After consent is obtained, the research team will notify the research pharmacy. The research pharmacy will be in possession of the randomization list and will determine which arm (intervention vs. placebo) the participant will be enrolled in.

4.4 Drug preparation and administration

The thiamine will be mixed in 50ml of normal saline and administered intravenously over 45-60 minutes. The placebo will be given using techniques and volumes matching those of the study medication.

All study medications will be continued for 3-days or until the participant expires.

4.4.1 Contingencies and Participant Withdrawal

- In the unlikely event that a participant is discharged alive from the hospital prior to 3 days after enrollment, all study medications will be stopped. The participant will remain in the study and will be followed for outcomes.
- If a patient is transferred to the hospital ward from the intensive care unit, the study drug will continue while the patient is in the hospital until 3 days.
- If the clinical team decides to give the participant vitamin B1 for clinical purposes, the study drug will be continued (including thiamine) as long as the total maximum dose of vitamin B1 is $\leq 1,500\text{mg/day}$. 1,500mg day is a standard dose for Wernicke's encephalopathy at many institutions and has not been associated with any increased harm.
- If a participant withdraws from the study, further administration of study meds will be stopped. Data collected prior to withdrawal will be maintained and the patient will be followed for outcomes, but additional data will not be collected.

4.5 Specimen collection procedures

4.5.1 Timing and volume of blood draw

All participants will have a blood samples collected at four time-points. Blood will be obtained by venipuncture, or from an existing venous or arterial catheter.

Specimen Collection Time Points

1. T1=0 hrs (just before study drug administration)
2. T2=24 hrs (+/- 4 hrs)
3. T3=48 hrs (+/- 4 hrs)

4. T4=72hrs (+/- 4hrs)

4.5.2 Specimen samples

At the T1, T2, T3, and T4 time points, blood will be sent for complete serum creatinine and a venous/arterial blood gas to measure lactate. These tests will be performed by the clinical laboratory at each site. As many of these laboratory tests are commonly obtained for clinical purposes, these tests do not need to be repeated if a result is available from the clinical care of the participant within 4 hours of the time point.

In addition to traditional clinical markers, 20ml of blood will be obtained for future biomarker analysis (including inflammatory biomarkers, markers of endothelial function, and markers of mitochondrial function), and thiamine levels.

4.6 General Sepsis Management

Investigators should follow local sepsis management guidelines. No specific sepsis bundle is required by this study, however the early administration of antibiotics, maintenance of a mean arterial pressure ≥ 65 mmHg with a combination of volume resuscitation and vasopressors, and early source control are recommended—as detailed in the Surviving Sepsis Guidelines.³⁹ Elements of sepsis care should be reported on the online case report form (CRF).

5. OUTCOMES

5.1 Definitions

5.1.1 Primary Outcome

The primary outcome will be creatinine change over the first 72-hours after enrollment with a focus on the 72-hour creatinine measurement.

5.1.2 Key Secondary Outcomes

- Incidence of Acute Renal Failure
- Length of ICU stay
- In-hospital Mortality
- Other biomarkers of renal injury (Serum cystatin C, NGAL, and KIM-1)
- Peripheral blood mononuclear cell mitochondrial oxygen consumption

5.2 Safety

5.4.1 Definitions

The following definitions will be used⁴⁰:

Adverse event: any untoward medical occurrence in a participant to whom a medicinal product is administered and which does not necessarily have a causal relationship with this treatment

Serious adverse event: any untoward medical occurrence that at any dose requires inpatient hospitalization or prolongation of existing hospitalization, results in persistent or significant disability or incapacity, results in a congenital anomaly or birth defect, is life-threatening, or results in death

Suspected unexpected serious adverse event: a serious adverse reaction, the nature, severity or outcome of which is not consistent with the reference safety information

5.4.2 Specific adverse event data collection

To assess specific and potentially serious adverse events that may be related to the study medication, we will collect data on the following:

Serious Adverse Event	Definition
Serious allergic reaction	Anaphylaxis or other allergic reaction requiring systemic corticosteroids. Allergic reaction should be related (or suspected to be related) to the study medication

5.4.3 Adverse Event Reporting

All unexpected serious adverse events thought to be related to the study drug, and any unexpected fatal or life-threatening adverse events thought to be related to the study drug will be recorded in the online CRF, reported directly to the coordinating center, and reported to the appropriate IRB shortly following the event per local protocol. In addition, unexpected serious adverse events related to the study drug will be undergo expedited reporting to the DSMB within 7 days of the coordinating center becoming aware of the event. The DSMB will additionally review all adverse events in aggregate after every 50 patients are enrolled.

Adverse events will additionally be reported to the FDA as outlined in 21CFR312.32 and summarized below:

- a. All unexpected fatal or life-threatening adverse events thought to be related to the study drug will be reported to the FDA within 7 calendar-days of when the TRPSS team is made aware of the event.
- b. All unexpected serious adverse events thought to be related to the study drug will be reported to the FDA within 15 calendar-days of when the TRPSS team is made aware.
- c. All serious unexpected adverse events, and any unexpected fatal or life-threatening events thought to be related to the study drug, will be reported back to all site investigators within 15 calendar-days of the event.
- d. The TRPSS team will periodically review all published information relating to the safety of each element of the drug combination. Any concerning safety information obtained from this review, or otherwise obtained (e.g. from unpublished scientific papers), will be reported to the FDA within 15 calendar-days.

6. SAMPLE SIZE CALCULATION AND STATISTICAL ANALYSIS PLAN

6.1 Sample size calculation

The planned sample size is based on the proposed primary outcome. In this longitudinal repeated measures study design, we have 4 time points, and are interested in measuring the effect of the intervention (thiamine) on the mean level of creatinine at the last time point (72-hours). We hypothesized that at 72-hours, the estimated mean difference (placebo-thiamine) would have similar magnitude as the pilot study's ⁴ observed mean difference (about 0.51). We used a linear mixed-effects model to estimate the parameters of the variance-covariance structure of the repeated measures data and used these estimates in obtaining the effect estimate of the mean difference at each of the 4 time points, with emphasis on 72-hours. We simulated the data using the estimated variance-covariance components from the pilot data which 0.19 for within-subject variance, and 1.3 for between-subject variance, and the estimated mean differences for the 4 time points from the pilot data. These data were put through a linear mixed effects model where linear contrasts were used for estimation at each time point. We then computed the non-centrality parameter and the corresponding F-statistic value. Together with the numerator and denominator degrees of freedom, the estimate of power at each time point was derived. Through different iterations of sample size, at N=80 (40 patients in each arm), we obtained a power of 0.80 at 72-hours. This method of power analysis for linear mixed-effects model was published in 2000.⁴¹ To account for drop-out and to

ensure adequate power at the end of the trial, we will plan to enroll a total of 88 patients (44 per arm).

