6.2 Statistical analysis plan

6.2.1 General considerations

The statistical analyses and reporting will adhere to the CONSORT guidelines.^{42,43} All tests will be two-sided, a p-value < 0.05 will be considered significant, and all confidence intervals will have 95% coverage. All analyses will be conducted on a modified intention-to-treat basis only including participants receiving at least the first dose of the study medications. In a double-blind trial, this approach is unbiased while increasing precision.⁴⁴ The two groups will be compared in relation to baseline characteristics using descriptive statistics.

The persons conducting the statistical analysis will be blinded to the randomized allocation. Groups will be designated as “A” and “B” until all pre-specified analyses are performed and shared with all authors and the Data Safety Monitoring Board.

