6.2.2 Creatinine at 72-hours

Assuming no unbalanced potentially confounding variables (as would be expected in this randomized trial), we will compare repeated measures of creatinine levels at each time point (0h, 24h, 48h, 72h) between arms using repeated measures analysis. A compound symmetry covariance structure will be used. If a patient receives renal replacement therapy or dies before any time point, creatinine levels will be imputed by carrying forward the last known value before the event. Study site will be controlled for as a fixed-effect in the regression model.

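### The 0.80 power at 40 per arm does not follow from the inputs in Protocol section 6.1: for the 72-hour mean creatinine level it names, they give about 0.45

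*Protocol*

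**What the plan says.** Section 6.1 states its target as the effect of thiamine on "the mean level of creatinine at the last time point (72-hours"). The assumed effect is the pilot's "observed mean difference (about 0.51"), placebo minus thiamine. The variance components, also from the pilot, are "0.19 for within-subject variance, and 1.3 for between-subject variance". The simulation used these together with "the estimated mean differences for the 4 time points from the pilot data", but only the 72-hour difference is printed. Power comes from linear contrasts at each time point and a non-central F distribution. The result is: "Through different iterations of sample size, at N=80 (40 patients in each arm), we obtained a power of 0.80 at 72-hours". Enrollment is then raised to 88 (44 per arm) to allow for drop-out.

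The test level is in section 6.2.1: "All tests will be two-sided, a p-value < 0.05 will be considered significant". On the analysis, section 6.2.2 says "we will compare repeated measures of creatinine levels at each time point" and "A compound symmetry covariance structure will be used".

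Sections 2.1 and 5.1.1 word the primary outcome as a change in creatinine from enrollment to 72 hours; 5.1.1 adds a focus on the 72-hour measurement.

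**The concern.** A between-subject variance of 1.3 is large next to a difference of 0.51. A comparison of levels at one time point carries all of that variance, and 40 per arm looks too few for 0.80 power. A change from baseline removes the between-subject part, so the two contrasts need very different sample sizes. Section 6.1 names the level, while the primary outcome is worded as a change.

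This power figure is the only justification given for the sample size. If it does not belong to the contrast it names, a null result on the 72-hour level would be read as coming from an 80%-powered comparison when the chance of detecting the assumed difference was under one half.

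**Working it through.** **Inputs.** Difference at 72 hours d = 0.51, within-subject variance 0.19, between-subject variance 1.3, n = 40 per arm (all section 6.1). Two-sided alpha 0.05 (6.2.1). Compound symmetry (6.2.2). Section 6.1 prints no denominator degrees of freedom, so both 78 (subjects minus 2) and 234 (3 × 78) are shown.

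**1. Attempt to reproduce 0.80 for the level at 72 hours.**
- Variance at one time point: 1.3 + 0.19 = 1.49.
- Variance of the between-arm difference: 2 × 1.49 / 40 = 0.0745, so SE = √0.0745 = 0.273.
- Non-centrality: 0.51² / 0.0745 = 0.2601 / 0.0745 = 3.49.
- Power from the non-central F with 1 numerator df: 0.454 (78 df) or 0.461 (234 df).
- Simulating the 72-hour comparison under compound symmetry (20,000 runs) gives 0.455.

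With complete data this contrast does not depend on the differences at 0, 24 and 48 hours.

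**2. What 0.80 would need for the level.**
- About 91 per arm (non-centrality 7.94, power 0.800 to 0.803); or
- a difference of about 0.77 at 40 per arm; or
- a total variance of about 0.65, which is half the between-subject variance alone.

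If all 44 per arm are analysed, non-centrality is 0.2601 / (2 × 1.49 / 44) = 3.84 and power is 0.49 to 0.50.

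**3. Rounding.** Taking each input at its favourable limit (0.515, 1.25, 0.185) gives 0.515² / (2 × 1.435 / 40) = 3.70 and power of about 0.48.

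**4. Other readings at 40 per arm with an effect of 0.51** (normal approximation).

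| Reading | Power |
|---|---|
| One-sided test of the level | 0.59 |
| Between-subject variance only | 0.52 |
| Average over the four time points | 0.50 |
| Components read as standard deviations | 0.41 |
| Change from 0 hours, no 0-hour difference (variance 0.38) | 0.96 |
| Baseline-adjusted 72-hour value (variance 0.356) | 0.97 |
| Within-subject variance only | above 0.99 |

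None gives 0.80. Values near it appear only with 80 per arm (0.81 with the between-subject variance only, 0.79 time-averaged), which contradicts the stated 40 per arm.

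**5. Change from 0 to 72 hours.** Its variance per patient is 2 × 0.19 = 0.38, so SE = √(2 × 0.38 / 40) = 0.138. The effect is 0.51 minus the 0-hour difference. That difference is not printed, so every value below is an assumption.

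| Assumed 0-hour difference | Effect on change | Power (78 / 234 df) |
|---|---|---|
| 0 | 0.51 | 0.955 / 0.958 |
| 0.10 | 0.41 | 0.836 / 0.842 |
| 0.12 | 0.39 | 0.798 / 0.804 |
| 0.20 | 0.31 | 0.603 / 0.610 |

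The change detectable with 0.80 power is about 0.39. These figures also rest on the correlation implied by the components, 1.3 / 1.49 = 0.87. With total variance held at 1.49, no 0-hour difference and 78 df, assumed correlations of 0.6, 0.7 and 0.8 give 0.54, 0.66 and 0.83; with a 0-hour difference of 0.10 they give 0.38, 0.48 and 0.65.

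**The case against.** The strongest reply is that section 6.1 opens by tying the sample size to the primary outcome, and that outcome is a change. On that reading 0.80 is attainable: a pilot 0-hour difference of about 0.12 gives it almost exactly. Section 1.5 reports that the earlier trial's arms were imbalanced in premorbid renal function, and the simulation used pilot differences at all four time points, so a nonzero 0-hour difference is plausible. It can be added that alpha and the covariance structure come from sections 6.2.1 and 6.2.2 rather than 6.1, and that stating 0.45 is of little use if the sponsor then chooses the change as the powered contrast.

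Part of this stands. The change reading cannot be excluded, and no shortfall is shown for it. But section 1.5 gives neither the size nor the direction of the imbalance, and premorbid function is not the 0-hour creatinine. The sentence that defines the target in 6.1 says mean level, its contrasts are taken at each time point, and section 6.2.2 compares levels. If the change was meant, that wording is wrong; if the level was meant, the 0.80 is wrong. Taking alpha and the covariance structure from neighbouring sections is an inference, but two variance components point to the same structure, and the choice of degrees of freedom moves power by less than 0.01.

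**Conclusion.** The concern holds. For the contrast that section 6.1 names, its own inputs give power of 0.45 to 0.46 at 40 per arm against the stated 0.80, and 0.49 to 0.50 if all 44 per arm are analysed. This rests on two-sided 0.05, compound symmetry and complete data. Neither rounding nor any alternative reading tried with an effect of 0.51 at 40 per arm recovers 0.80.

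The conclusion is confined to the level. Whether 0.80 holds for the change cannot be checked, because it turns on an unprinted 0-hour difference. As written, the protocol does not let a reader say which contrast has 0.80 power or what difference the trial can detect. This must be corrected.

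**What to change.** Leave the sample size unchanged and revise section 6.1:

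1. Withdraw 0.80 as the power for the 72-hour mean level and state about 0.45 at 40 per arm.
2. Name one powered contrast that agrees with both the primary outcome (2.1, 5.1.1) and the analysis in 6.2.2. A change or a baseline-adjusted 72-hour difference is one option, and is much more precise under the stated variances (SE 0.138 for the change against 0.273 for the level).
3. Print the four assumed mean differences, including the one at 0 hours.
4. Give the recomputed power and the detectable difference for the named contrast, in a short table over the assumed 0-hour difference and the correlation between the 0- and 72-hour values.

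The cost is rewording and a re-run of the existing power program; no extra patients are needed. The downside is that the restated power for a change or baseline-adjusted contrast depends on those two assumptions and may fall below 0.80.
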